8.2 Adjustments for Covariates

Adjustment for covariates is not planned for this study.

8.3 Handling of Dropouts or Missing Data

Due to the early termination of study enrollment missing data will not be imputed as there is no need to assess the robustness of the primary analysis by evaluating the impact of missing data.

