### **3.7 SUBJECT WITHDRAWAL**

All subjects should be encouraged to remain in the trial throughout the entire follow up time period. If a subject decides to discontinue trial participation, the reason for their discontinuation must be recorded in the medical record and submitted via the eCRF. Subjects who discontinue participation prematurely will be included in the analysis results if the 9-month visit has been reached.

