## 5.0 STATISTICAL CONSIDERATIONS AND ANALYSIS PLAN

### 5.1 ASSUMPTION OF PRIMARY ENDPOINT RATE

The endpoints will be tested in a sequential manner:

1) Functional Endpoint

Assessment of primary patency rate at 9-months, defined as continuous patency without the occurrence of a total occlusion of the original lesion, without a re-intervention to treat a partial or total occlusion of the stented segment, or bypass of the stented segment due to clinically-driven restenosis or occlusion.

Followed by:

2) Clinical Endpoint

Improvement in systolic blood pressure (SBP) at 9-months as compared to baseline systolic blood pressure.

If the null hypothesis for the functional goal is rejected at the 0.025 level of significance, the null hypothesis for the clinical goal will be tested at the 0.025 level. If rejected, success will be declared for both Performance Goals. Otherwise, if only the first (primary patency) null hypothesis can be rejected, success will be declared only for that Performance Goal. This sequential approach controls the overall significance level at 0.025. Of note, no success can be declared if the null hypothesis for the primary patency goal was not rejected, regardless of the outcome for the other Performance Goal.

For the primary patency endpoint, the proportion of subjects experiencing this outcome will be compared to the predefined Performance Goal of 0.70. Formally, the hypothesis to be tested is:

$H_0$ : The incidence  $p_{PP}$  of primary patency at 9-months is less than or equal to 0.70.

$H_0$ :  $p_{PP} \leq 0.70$

$H_A$ : The incidence  $p_{PP}$  of primary patency at 9-months is greater than 0.70.

$H_A$ :  $p_{PP} > 0.70$

The derivation of the Performance Goal is described in Section 5.2.1 Derivation of the Performance Goal for Patency.

For the SBP endpoint, the change between SBP from baseline to 9-month follow-up will be compared to a predefined Performance Goal of 10mmHg. Formally, the hypothesis to be tested is:

$H_0$ : The mean difference between SBP at 9-months and baseline,  $\mu_{\Delta\text{SBP}}$ , is less than or equal to 10mmHg.

$$H_0: \mu_{\Delta\text{SBP}} \leq 10\text{mmHg}$$

$H_A$ : The mean difference between SBP at 9-months and baseline,  $\mu_{\Delta\text{SBP}}$ , is greater than 10mmHg.

$$H_A: \mu_{\Delta\text{SBP}} > 10\text{mmHg}$$

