Both primary endpoints will be tested in one-sided fashion against a significance level of 0.025; the primary patency endpoint will be tested using exact binomial methods and the SBP endpoint will be tested using a paired t-test.

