## 5.2 SAMPLE SIZE

For a one-sided alpha of 0.025 and desired power of 87%, sample size for the primary patency endpoint is established by assuming a hypothesized primary patency incidence of 0.82, which gives 125 evaluable subjects therefore, accounting for 10% attrition, 138 subjects are needed for this endpoint. At the proposed evaluable sample size of 125, no more than 27 subjects (22%) can fail primary patency in order to meet the endpoint hypothesis.

For the endpoint of reduction in SBP, we assume an average reduction of 13.7mmHg. Under a hypothesized standard deviation of 12mmHg for a difference in SBP there will be 92% power to meet the Performance Goal. This standard deviation is conservatively approximated based on the expected range of SBP at baseline of 155mmHg to 180mmHg divided by 3 and assuming a similar standard deviation at the 9-month follow up. A mean difference in SBP at 9-months of 12mmHg will be required in order to reject the null hypothesis at a one-sided alpha of 0.025 at the proposed sample size.

The primary endpoints of primary patency and reduction in SBP are powered at 87% and 92%, respectively, in order to maintain the overall trial power at 80% to meet both endpoints.

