### 5.3.6 ADDITIONAL ANALYSES

#### 5.3.6.1 SENSITIVITY ANALYSIS

For primary patency, a tipping point analysis will be conducted in order to assess the effect of missing data on the analysis. Results from imputing all possible combinations of successes and failures for the missing data will be summarized.

For the SBP endpoint, as a best/worst case analysis, the largest/smallest drop in SBP seen in the complete data will be filled in for the missing values. Summary statistics for the resulting mean difference and p-values from the primary hypothesis test will be presented. In addition, multiple imputations will be used by substituting imputed SBP at 9-months based on available baseline characteristics (including baseline SBP) and then recalculating the mean differences, presenting summary statistics and the p-value for the primary hypothesis.

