9.9 Analysis of Primary Endpoints

Statistical tests relating to the primary endpoints will be one-sided with p-values less than 0.025 deemed significant.

Amendment #1: 15Jul13

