9.9.1. Primary Patency Analysis

The primary endpoint will be the cumulative incidence of primary patency at 9-months of study computed as the number of subjects with primary patency at 9-months divided by the number of subjects in the ITT population. An exact binomial one-sided 95% confidence interval will be constructed and the upper limit compared to the Performance Goal equal to 70%. A p-value for the one-sided exact test of the difference between the observed rate and the Performance Goal will be presented. The primary analysis will be analyzed with observed data only.

A planned subgroup analysis of the primary functional endpoint will be performed (details are provided in section 9.9.4

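### The SAP cancels the protocol's missing-data analyses for a reason that does not follow, and the documents contradict each other on whether and how subjects who leave before month 9 count in the patency analysis

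*SAP*

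**What the plan says.** **Missing-data analyses.** For patency, Protocol 5.3.6.1 says "a tipping point analysis will be conducted in order to assess the effect of missing data on the analysis", run over every combination of success and failure. For SBP the same section plans a best/worst-case fill-in and multiple imputation. SAP 2, 6.2 and 8.3 withdraw these. SAP 8.3 gives the reason: after early termination of enrolment, "missing data will not be imputed as there is no need to assess the robustness of the primary analysis". SAP 6.2 and 9.9.3 keep one sensitivity analysis, in the per-protocol population.

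**Early leavers.** Protocol 3.7 says: "Subjects who discontinue participation prematurely will be included in the analysis results if the 9-month visit has been reached". SAP 9.9.1 says: "The primary analysis will be analyzed with observed data only". The same SAP section also divides by all subjects in the intent-to-treat (ITT) population. SAP 7.6.1 defines patency by events (no total occlusion, no qualifying re-intervention or bypass) and calculates it per lesion.

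**What remains.** SAP 7.4 promises a supportive time-to-event analysis of the primary efficacy endpoint. The only one specified, in SAP 9.11.11, concerns revascularization of the target vessel, with lesions censored at last contact.

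**Status of the tests.** SAP 2 and 8.7 call the inference descriptive. SAP 9.9 nevertheless keeps primary-endpoint tests that are "one-sided with p-values less than 0.025 deemed significant".

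**The concern.** The reason given for cancelling the analyses does not support cancelling them. Ending enrolment early does nothing to reduce the share of subjects with missing outcomes, and it raises the weight of each one. The SAP is also at odds with itself: 8.3 sees no need to assess robustness, while 9.9.3 still sets out to assess it. The tool it keeps, the per-protocol set, removes further subjects and asks nothing about those whose outcome is unknown, so it cannot show dropout bias.

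The second problem is classification. Take a lesion that occludes or is re-intervened at month 4 in a subject who then leaves the trial. Under the event-based definition its outcome is known: failure. No section says that it must be counted. If the month-9 rule and the observed-data sentence are taken together, it may be left out, and patency is biased upward. If the ITT denominator governs, every leaver counts as a non-success, including those whose lesions were patent when last seen. The choice could be made after the data are seen.

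**Working it through.** **Inputs.** Exact binomial test (Protocol 5.1: "the primary patency endpoint will be tested using exact binomial methods"), "compared to the predefined Performance Goal of 0.70", one-sided alpha 0.025 (Protocol 5.1, SAP 9.9). Design rate: "assuming a hypothesized primary patency incidence of 0.82" (Protocol 5.2). Planned attrition 10% and 138 enrolled (Protocol 5.2). Actual enrolment 68 (SAP 6.1). The documents give no actual dropout or lesion count.

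**The plan's own figure.** The test passes with r successes in n if P(X ≥ r | n, 0.70) ≤ 0.025. At n = 125:
- 98 successes (27 failures): p = 0.0230, power at 0.82 = 0.876
- 97 successes (28 failures): p = 0.0368, not a pass

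This reproduces the stated limit of 27 failures and the 87% power.

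**Weight of one outcome.** 1/138 = 0.7% as planned; 1/68 = 1.5% now; ratio 138/68 = 2.0.

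**Illustration.** Assume 10% attrition and one lesion per subject: 68 × 0.90 = 61.2, so 61 observed and 7 missing. At n = 61 the test passes with at most 11 failures (50/61, p = 0.0248; 49/61, p = 0.0486). Then add omitted lesions as failures:

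| Observed | Rate | p | Added failures that reverse the pass | p if all 7 failed (n = 68) |
|---|---|---|---|---|
| 50/61 | 82.0% | 0.0248 | 1 (50/62, p = 0.0414) | 0.312 |
| 51/61 | 83.6% | 0.0115 | 2 | 0.224 |
| 52/61 | 85.2% | 0.0048 | 3 | 0.151 |
| 53/61 | 86.9% | 0.0018 | 4 | 0.095 |
| 54/61 | 88.5% | 0.0006 | 6 | 0.056 |
| 55/61 | 90.2% | 0.0002 | 7 | 0.030 |
| 56/61 | 91.8% | <0.0001 | not reversed | 0.015 |

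So passes with 6 to 11 failures can be reversed, and passes with 5 or fewer cannot. At a true rate of 0.82 and n = 61, P(pass) = 0.582 and P(pass with 6 to 11 failures) = 0.556, which is 0.556/0.582, or about 96% of passes. P(exactly 11 failures), where one more decides it, is 0.13.

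**The two denominators.** With 50 observed successes, observed data only gives 50/61 (82.0%, p = 0.0248). The full ITT denominator gives 50/68 (73.5%, p = 0.312).

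**Dependence on n.** Adding one failure to the weakest passing result:

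| Observed n | Basis | Before | After one added failure | Reversed? |
|---|---|---|---|---|
| 54 | 20% attrition | 45/54, p = 0.0193 | 45/55, p = 0.0344 | yes |
| 58 | 15% attrition | 48/58, p = 0.0201 | 48/59, p = 0.0349 | yes |
| 61 | 10% attrition | 50/61, p = 0.0248 | 50/62, p = 0.0414 | yes |
| 65 | 5% attrition | 54/65, p = 0.0121 | 54/66, p = 0.0213 | no |
| 73 lesions | 68 × 0.9 × 1.2 = 73.4 | 60/73, p = 0.0130 | 60/74, p = 0.0220 | no |
| 74 lesions | one lesion more | 60/74, p = 0.0220 | 60/75, p = 0.0353 | yes |

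The 1.2 lesions per subject is the outside figure cited in SAP 5.2.

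**The case against.** A reader might infer three stronger claims. The documents do not support them.

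- *Early leavers are dropped.* This is not settled. Protocol 3.7 says when early discontinuers are included; it does not say only then, and it follows a sentence about subjects who choose to stop, so its reach to deaths is unclear. SAP 9.9.1 divides by the whole ITT population, which would push patency down. Because the endpoint is event-based, a recorded month-4 failure can itself be called observed data. What stands is a contradiction with several readings.
- *No analysis is left that would show the problem.* Some remain. The time-to-event analysis counts a month-4 revascularization even if the subject later leaves. Clinically driven target lesion revascularization is computed over all ITT subject-lesions (SAP 7.6.2). Observed and expected visits are tabulated (SAP 9.1), so the amount of missingness will be visible. But the analysis in SAP 9.11.11 does not treat an untreated occlusion as an event, and censoring at last contact assumes that leaving is unrelated to failure. It does not replace a tipping-point table.
- *One lost failure flips the result.* This is true only at the boundary and for some sample sizes. The illustration counts one lesion per subject, whereas patency is analysed per lesion. It also applies only the p < 0.025 rule: at 50/62 the lower limit of an exact one-sided 95% interval is 0.705, still above 0.70.

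The strongest defence is that all inference is declared descriptive and that the changes are openly listed as deviations. This lowers the severity. It does not remove the point: p < 0.025 is still to be called significant, and a descriptive patency estimate is just as biased if failures go missing.

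**Conclusion.** The point holds at moderate severity. The cancellation of the tipping-point, best/worst-case and multiple-imputation analyses is plain in the text, and the reason given for it does not follow. The handling of early leavers is contradictory between Protocol 3.7, the two statements in SAP 9.9.1 and the definition in SAP 7.6.1. The direction of any bias depends on which of them is applied.

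On size, with 61 observed and 7 missing, missing outcomes could reverse any nominal pass with 6 to 11 failures, and the same 50 successes read as 82.0% or 73.5% depending on the denominator. This rests on an assumed 10% attrition at 68 enrolled and one lesion per subject. Reversal of the higher passes needs most or all of the missing lesions to have failed, so these figures show what could happen and do not predict it. For SBP the loss of the planned analyses is equally clear, but the documents give no data from which to size it.

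**What to change.** 1. State in SAP 7.6.1 and 9.9.1 that any lesion with a documented endpoint-defining failure (total occlusion, or re-intervention or bypass meeting the SAP 7.6.1 definition) before the 9-month window closes counts as a failure, whatever the later follow-up.
2. Reconcile Protocol 3.7 with the two statements in SAP 9.9.1 so that one per-lesion denominator applies, with an explicit rule for lesions whose month-9 status is unknown.
3. Reinstate the protocol's tipping-point table for patency and its best/worst-case and multiple-imputation analyses for SBP, reported descriptively, and delete the statement that robustness need not be assessed.

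The cost is SAP wording and a few programmed tables. No new data are needed.

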8.4 Interim Analyses and Data Monitoring

No formal statistical rule for stopping the trial will be defined in this trial and no formal interim analysis for efficacy is planned.

Periodic meetings for the independent Data Safety Monitoring Board (DSMB) will be held at which the DSMB members will evaluate interim data to determine any specific safety concerns.

Amendment #1: 15Jul13

Confidential

The DSMB is composed of at least three members which include physicians with specialization in the field of this trial and a biostatistician. They are independent and not directly involved in the conduct of the trial. The DSMB will review the trial on a periodic basis as defined in the DSMB Charter.

Based on the safety data, the DSMB may recommend to Atrium to modify or stop the trial. All final decisions, however, regarding trial modifications, rest with Atrium.

8.5 Clinical Events Committee (CEC)

The Clinical Events Committee (CEC) is made up of physicians with specialization in the field of this trial who are not participants in the trial. The CEC is charged with the development of specific criteria used for adjudication of clinical events related to the primary endpoints in the trial.

At the onset of the trial, the CEC will develop a CEC Charter which will describe explicit rules outlining the minimum amount of data required, and the algorithm followed in order to classify a trial endpoint related clinical event. The CEC will meet regularly (at a minimum of once per year) to review and adjudicate trial endpoint related clinical events in which the required minimum data is not available. The CEC will also review and rule on all deaths that occur throughout the trial.

Once the specific criteria for clinical events and endpoints are established, the CEC will be responsible for adjudicating all clinical events when all necessary data are available.

Details regarding event adjudication are provided in the CEC Charter.

8.6 Multi-Center Studies and Pooling of Centers

Due to the early termination of study enrollment, pooling of centers will not be carried out as the patient-distribution across sites within the same geographical area might not meet pooling requirements.

8.7 Multiple Comparisons/Multiplicity

Due to early termination of study enrollment, the results from the primary and secondary efficacy analyses will be interpreted descriptively and therefore the analysis will not be adjusted to control the Type I error.

8.8 Unit of Analysis

For the primary functional endpoint of primary patency rate the unit of analysis is the atherosclerotic lesion(s). The rationale for analyzing the primary endpoint following a per lesion approach, is to avoid overestimation of the failure rate, as more lesions would be at risk for restenosis but would not be accounted for in a per subject analysis.

Since blood pressure is measured on the subject level, the primary clinical endpoint of change SBP will be evaluated at the subject level.

9. STATISTICAL ANALYSIS

9.1 Disposition of Subjects

The number of subjects screened, enrolled, and number of subjects who underwent the procedure but never received a study stent will be summarized. Also, the number of implanted subjects who completed the study, the number of implanted subjects who discontinued from the study, and the reasons for study discontinuation will also be summarized at minimum.

In addition, the number of subjects with an observed (within visit window), observed (regardless of visit window) and expected visit will be presented at each follow-up time point.

A subject listing will be provided and include at minimum the subject ID, informed consent date, procedure date, completion status, date of completion/discontinuation, last visit completed, per-protocol population exclusion, and reason for study discontinuation.

9.2 Protocol Deviations

A protocol deviation is defined as an event where the Investigator or investigational site personnel did not conduct the trial according to the protocol.

Protocol deviations were classified as major if the parameter affected one of the primary endpoints. All other protocol deviations which did not directly affect the collection or analysis of primary endpoint information were considered minor protocol deviations.

The number and percentage of subjects with major and minor protocol deviations will be summarized for all subjects in the ITT analysis population. A subject listing of all protocol deviations will be provided that includes the date of the deviation, the deviation description, the classification of whether the deviation was judged to be major or minor and an indicator for exclusions from the per protocol (PP) analysis population.

9.3 Analysis Population

Intent-to-Treat (ITT) Analysis Population: All subjects enrolled in the study will be included in the ITT analysis population. This will be the primary analysis population.

Per Protocol (PP) Analysis Population: All subjects enrolled in the study, who receive the study device as intended with no major protocol deviations will be included in the per protocol analysis population.

9.4 Demographic and Other Baseline Characteristics

The demographic and baseline characteristics of the subjects will be summarized for all subjects in the ITT analysis and the per protocol populations. All subjects enrolled will be included in a listing. Quantitative data (i.e., age, height, weight and body mass index (BMI)) will be summarized using descriptive statistics (i.e., number of subjects (N), mean, standard deviation (SD), first quartile (Q1), median, third quartile (Q3), range (minimum, maximum). Age will be reported in years and is to be calculated based on the date of informed consent using the following formula:

Amendment #1: 15Jul13

Age = ((informed consent date – date of birth + 1) / 365.25) truncated as an integer

Age will also be categorized as follows: <65 years and ≥65 years. Qualitative data (i.e., gender, ethnicity, race, age category) will be summarized using frequency counts and percentages.

The number and percent of subjects with abnormal physical examination findings at baseline will be summarized.

Variables to be included in the demographic and baseline characteristics summaries/listings include:

1. Age
2. Age group (>=18 - <65 years and >=65 years)
3. Gender
4. Race
5. Ethnicity
6. Number of lesions
7. Pulse
8. Oral temperature (celcius)
9. Respiratory rate (breaths/minute)
10. Systolic blood pressure (mmHg)
11. Diastolic blood pressure (mmHg)
12. Height
13. Weight
14. BMI (kg/m²)

9.5 Targeted Medical History

A focused medical history will be reviewed and recorded for each subject at or prior to the baseline visit.

Medical history information includes:

- Previous treatment for Artherosclerosis Renal Artery Stenosis (ARAS)

Amendment #1: 15Jul13

Confidential

- Previous bypass
- Previous surgery
- Time from most recent surgery
- Ballon Angioplasty (PTRA)
- Bare metal stent
- Time from most recent bare metal stent
- Previous contralateral vessel
- Target vessel
- Other treatments
- History of renal insufficiency
- History of hyperlipidemia
- History of smoking
- History of diabetes mellitus
- History of Coronary Artery Disease (CAD)
- History of other artery disease (aortic disease, congenital heart disease, other)
- History of Myocardial Infarction (MI)
- Type of MI
- History of Congestive Heart Failure (CHF)
- New York Heart Association (NYHA) Classification
- Previous Percutaneous Coronary Intervention (PCI) or angioplasty
- Previous Coronary Artery Bypass Surgery (CABG)
- Time from most recent CABG
- History of arrhythmia
- History of stroke
- Time from most recent stroke
- History of Transient Ischemic Attack (TIA)
- Time from most recent TIA
- History of peripheral vascular disease
- Previous peripheral artery revascularization/surgery
- Time from most recent revascularization/surgery
- Previous procedures

Amendment #1: 15Jul13

Confidential

- History of flash pulmonary edema
- History of fibromuscular dysplasia

In addition, the medical history information will be provided as a subject listing.

9.6 Anti-hypertensive Medical History

Anti-hypertensive medical history will capture up to three months' information prior to screening to document that reasonable and aggressive efforts were previously made to manage hypertension via a broad variety of medications that have been tried and failed. The data will be summarized and include:

- Number of subjects taking diuretics
- Number of subjects taking an Angiotensin Coverting Enzyme (ACE) inhibitor or Angiotensin Receptor Blocking (ARB) agent
- Number of subjects taking a beta blocker or calcium channel blocker
- Time from diagnosis

